2.3 Microbiome Sub-Study

Aim 1: To identify earlier (4-weeks post TQD) and persistent (8-weeks post TQD) smoking cessation associated changes in gut microbiome composition and function.

H1a: Smoking cessation will result in decreases in *Prevotella* and *Bacteroides* species from the *Bacteroidetes* phylum, decreases in β - and γ - *Proteobacteria*, increases in *Clostridium* clusters IV and XIV from the *Firmicutes* phylum, and increases in *Bifidobacteria* and HGC bacteria from the *Actinobacteria* phylum.

H1b. We expect to observe decreases in neurotransmitters implicated in reward (dopamine, serotonin, GABA) as well as their precursors (tyrosine, tryptophan, glutamate), and microbial metabolites involved in appetite regulation (indole and propionate).

Aim 2: To evaluate the relationship between post-cessation changes in the gut microbiome, dietary intake, and smoking abstinence.

H2: Greater post-cessation changes in the gut microbiome will predict increased dietary intake and lower smoking abstinence rates 12 weeks post TQD.

[figure not shown]
Aim 3: To explore whether BAS+ (vs. SC) mitigates the effect of gut microbiome changes on dietary intake and smoking abstinence.

H3: Because BAS+ promotes alternative, non-food sources of reinforcement, BAS+ (vs SC) will mitigate the effects of microbiome changes on dietary intake and smoking abstinence 12 weeks post TQD.

3 Study Design

3.1 General Design - Parent (Main) Study

This is a randomized clinical trial of the efficacy of BAS+ plus TN compared to SC plus TN in treatment-seeking smokers. After completing an Intake Visit (~week -3), eligible smokers will be randomized (stratified by nicotine dependence, BMI and gender) to participate in 8 individual sessions of BAS+ or SC over a 10-week treatment period with two sessions prior to the target quit date (weeks -2, -1) and six sessions post-target quit date (TQD [week 0] and weeks 1, 2, 4, 6, and 8). Standard, 8-week; open-label TN will begin on the TQD. Moderators will be assessed pre-treatment. Mediating mechanisms will be assessed before, during, and at the end of treatment (EOT, week 8). Smoking will be assessed by self-report and biochemically confirmed (Carbon Monoxide [CO] < 5 or absence of Urine Cotinine) at all in-center visits (for CO ONLY) after quitting, at EOT (week 8), and at the 12- and 26-week follow-ups. Weight will be assessed at these same time points. Food intake will be measured by three consecutive days of 24-hour food recalls at Baseline [week -2] and 4-, 8-, and 12- and 26-weeks post-TQD. Smoking cessation and PCWG are the primary outcomes and food intake is a secondary outcome at 26-weeks post-TQD. Consistent with intent-to-treat (ITT) analyses, we will measure smoking cessation and weight gain in the full sample at the 26-week follow-up, evaluating a smoking status by treatment interaction for the PCWG analysis.

Time points (i.e. study weeks) displayed in Figure

[figure not shown]
CONFIDENTIAL

This material is the property of the University of Pennsylvania. Do not disclose or use except as authorized in writing by the study sponsor

1 and included within the Study Procedures Section represent approximations. Participants will follow a study schedule similar to that designated in Figure 1 and the Study Procedures, but will be permitted a degree of flexibility based on the maximum/minimum amount of time allowed between each time point established by the Principal Investigator. If a participant is unable to attend an in-person visit within the permissible window of time allotted between time points, counseling and applicable study measures may be completed/collected via telephone. In-person completion of the Intake and Baseline Visits are considered mandatory for study participation.

3.2 General Design - Neuroimaging Sub-Study

We propose to study a sub-sample of consecutively recruited participants (N=~50) enrolled in the parent randomized clinical trial. As displayed in **Figure 2**, an equal number of fMRI eligible smokers from the BAS+ or SC treatment group will be studied before treatment (~week -2) and during the final week of nicotine patch therapy (~week 7-8). As part of the parent study, smoking will be assessed by self-report and biochemically confirmed weekly after quitting, at EOT (week 8), and at the 12 and 26 week follow-ups. Weight will be assessed at these same time points. Food intake will be measured by three consecutive days of 24-hour food recalls at baseline and 4-, 8-, 12- and 26-weeks post-TQD.

Scans identified in **Figure 2** and included within the Study Procedures Section represent approximations. Participants will complete scans as designated in Figure 2 and the Study Procedures, but will be permitted a degree of flexibility at the discretion of the Principal Investigator due to extenuating circumstances.

3.3 General Design - Microbiome Sub-Study

We will study a subsample of up to 60 consecutively recruited smokers enrolled in the parent trial. The microbiome study subgroups will be balanced for age, sex, and BMI. In addition to the exclusion criteria for the parent trial, we will exclude individuals with current and recent (last 3 weeks) use of non-topical antibiotics, antifungals, antivirals, and psychotropic drugs. Participants who are initially eligible based on telephone screening will complete an in-person Intake session as part of the parent study. Before or during the Intake session, consent for participation in the sub-study will be obtained and final sub-study eligibility will be confirmed. An equal number of microbiome eligible smokers from the BAS+ or SC treatment groups will be instructed to provide a stool sample on **Week -2 (Baseline Visit)**, **Week 4 (Mid-Tx 3 Visit)**, and **Week 8 (End of Treatment Visit after completing TN treatment)**. Participants will be instructed to collect a stool sample within 24 hours (up to ~36 hours is permissible) of the target time points. Directions and supplies for stool specimen collection will be provided at the visit prior to collection.

We will assess within-subjects changes in the gut microbiome across time and explore between treatment group comparisons at week 12. As part of the main study, smoking is assessed by self-report and is biochemically confirmed (CO < 5) weekly after quitting, at EOT (week 8), and at the 12- week follow-up. Food intake is measured by three consecutive days of 24-hour food recalls at baseline and 4- 8- 12- week post-TQD.

CONFIDENTIAL

This material is the property of the University of Pennsylvania. Do not disclose or use except as authorized in writing by the study sponsor

3.4 Study Duration – Parent (Main) Study

Recruitment/enrollment began in earnest in September 2016 and will continue for ~44 months. We anticipate that ~340 participants will have completed the study by December 2020. We estimate that it will take ~30 weeks/8 months for a participant to complete the entire study.

3.5 Study Duration- Neuroimaging Sub-Study

Recruitment/enrollment for the neuroimaging sub-study is anticipated to begin in late July or August 2017 and will continue for ~18 months. We estimate that up to 50 participants will have completed the neuroimaging sub-study by ~April 2019. We estimate that it will take ~10 weeks/2.5 months for a participant to complete the neuroimaging sub-study (i.e. both fMRI scans).

3.6 Study Duration- Microbiome Sub-Study

Recruitment/enrollment for the microbiome sub-study is anticipated to begin in late September or October 2019 and will continue for ~8-10 months. We estimate that up to 60 participants will have completed the microbiome sub-study by ~July 2020.

4 CHARACTERISTICS OF THE STUDY POPULATION

4.1 Target Population

Participants will be treatment-seeking males and females between the ages of 18-65 who report smoking at least 5 cigarettes/day for at least the past 6 months.

4.2 Accrual - Parent (Main) Study

We will enroll ~625 participants (i.e., provide consent) to achieve a sample of ~340 who enter treatment (i.e., randomized) and remain enrolled through the 26-week assessment. To achieve this goal over a ~44-month enrollment period, we will complete 55 telephone screens monthly to obtain 25 smokers who meet criteria. Of these smokers, we expect ~15 to attend the Intake Visit, and ~10 per month to be confirmed eligible to be randomized after completing the Intake Visit.

In order to increase retention throughout the study we will: (1) educate subjects about the benefits of participation and the knowledge gained from the study; (2) schedule sessions at times convenient for participants; (3) provide reminder calls; and (4) provide payment for completion of all study visits. As is the convention in smoking cessation trials, smokers who are lost to follow-up will be included in the analysis and counted as smokers.

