4.8.1 When and How to Withdraw Subjects

Subjects are free to withdraw from the study at any time. Subjects may be deemed "ineligible" at any time per the exclusion criteria listed in section 4.5. No follow-up data collection is required for participants who withdraw or are deemed ineligible throughout the study.

5 Study Drug (Transdermal Nicotine [TN])

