6.5.6 Outcomes

Weight: Weight (primary outcome) will be measured by a physician's scale (pounds) at the beginning of every in-person visit. Participants will be wearing light clothing without shoes. Pre-cessation weight will be computed as the average of weights at the Intake and Baseline Visits prior to any change in smoking behavior. Weight change from Baseline to the 26-week follow-up will serve as a primary weight outcome variable.

Food Intake (24-Hour Dietary Recalls): Food intake (secondary outcome) will be assessed via 3 telephone-administered, 24-hour dietary recalls during the week after (or near) the Baseline, Mid-Treatment 3 (week 4), End of Treatment (week 8) and the 12-week and 26-week follow-up visits (n=15). A trained member of the research staff will use a multi-pass method with an interactive computerized software program, the ASA24® (Automated Self-Administered 24-hour Recall), to determine total kcal/day (outcome variable). The ASA24® was created by investigators at the NCI. Three recalls are considered optimal for assessing dietary intake, especially when weekend and weekdays are assessed, as we propose to do when possible. If participants are unable to complete a scheduled recall over the telephone or are onsite for a scheduled visit, participants may be asked to complete a 24-hour dietary recall with the research staff in-Center. Comparable accuracy can be achieved when administered in-person and over the telephone. Food recalls are widely used, reliable and valid, assessing kcals/day within 10% of actual dietary intake measured under laboratory observation and by doubly labeled water.

Changes in food intake (kcals) from baseline to week 12 will serve as an outcome for the microbiome sub-study.

Smoking Cessation (CO, Urine Cotinine, and Saliva Cotinine): Smoking abstinence (primary outcome) will be assessed and biochemically verified at EOT (week 8), at 12 and 26 weeks after the target quit date. The primary smoking outcome variable will be 7-day point prevalence abstinence (no smoking, not even a puff, for at least 7 days prior to the assessment) biochemically verified by CO < 5 ppm or Urine Cotinine assessment at a sensitivity of 100 ng/mL at EOT (week 8) and Follow-Up 1 and 2 visits (Week 12 and Week 26). Smoking status will also be biochemically confirmed by saliva cotinine < 15ng/ml at the 12- and 26-week follow-up.

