6.7 Sample Size Determination- Parent (Main) Study

For **Aim 1** we hypothesize that BAS+ vs. SC will have higher smoking abstinence rates and less PCWG at the 26-week follow-up (primary outcomes). Power calculations were all approximated as t-tests or z-tests, and conducted using PASS Software (Power and Sample Size, NCSS Software, Kaysville, UT), Bonferroni corrected for two primary outcomes ($p=.025$). Proportions of abstinent and smoking subjects will be compared using the log of the odds-ratio, which has a known variance. Informed by smoking cessation counseling plus TN research, we anticipate that the 6-month abstinence rate will be 13% in the SC (control) group and 25% in the BAS+ group (consistent with a persistent effect of BAS+ after the discontinuation of TN). A sample of 213 per group provides 82% power to detect this 12% difference in quit rates at 6 months. This represents a clinically meaningful effect and corresponds to a small effect size ($\delta=.15$). For PCWG, we will include all participants in the analysis, while testing a smoking status x treatment interaction. Informed by epidemiological and clinical studies of PCWG, we will have 80% power to detect a 6 pound (2.72 kg) difference in PCWG between BAS+ and SC, using the interaction term. We expect BAS+ vs. SC will have less post-cessation food intake (secondary outcome) at the 26-week follow-up. We have 80% power to detect a 320 kcal/day difference between the two groups ($p = .05$). In light of these considerations (i.e., 213 subjects per arm; total 426) and an attrition estimate of 15% across accrual, we will recruit a total of 245 subjects to each arm for a total of 490 subjects (~500).

For **Aim 2**, we hypothesize that BAS+ vs. SC, will increase alternative reinforcers, and reduce food reward, the RRVF, and food cue-induced craving. These changes, in turn, will predict less food intake and PCWG, and greater smoking abstinence at the 26-week follow-up. Using structural equation modeling, we will test the treatment effect on the slope of the mediators versus time, with pre-quit values representing the intercepts. We will examine the proportion of

CONFIDENTIAL

This material is the property of the University of Pennsylvania. Do not disclose or use except as authorized in writing by the study sponsor

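### Sections 3.4 and 4.2 plan about 340 participants at week 26, but section 6.7 computes power on 426; the stated food-intake power fails at 340 and weight power is lower too

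*Combined protocol and SAP*

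**What the plan says.** Two sections give the smaller number. Section 4.2 sets accrual "to achieve a sample of ~340 who enter treatment (i.e., randomized) and remain enrolled through the 26-week assessment", from about 625 consents. Section 3.4 says: "We anticipate that ~340 participants will have completed the study by December 2020". The recruitment flow in section 4.2 is stated in the same terms: "To achieve this goal over a ~44-month enrollment period", the plan expects 15 Intake attendees per month and about "10 per month to be confirmed eligible to be randomized after completing the Intake Visit".

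Section 6.7 gives the larger number: "A sample of 213 per group provides 82% power to detect this 12% difference in quit rates at 6 months". The same section claims 80% power for a 6 lb (2.72 kg) difference in weight gain, through the smoking-status-by-treatment interaction, and 80% power for 320 kcal/day in food intake. From 426 in total and 15% attrition it arrives at 245 per arm, 490 overall (rounded to about 500).

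Three other statements decide which number matters for which outcome. For abstinence, section 4.2 says that "smokers who are lost to follow-up will be included in the analysis and counted as smokers". For weight, section 6.5.6 says: "Weight change from Baseline to the 26-week follow-up will serve as a primary weight outcome variable". And section 4.8.1 says: "No follow-up data collection is required for participants who withdraw or are deemed ineligible throughout the study".

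**The concern.** The planned number at week 26 is about 20% below the number on which power was computed (340/426 = 0.80). No section connects them, gives power for 340, or states how many must be randomised to yield 340. A reader cannot tell whether the randomised target is 400, 417, 440 or 490, and so cannot judge whether the trial reached it.

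The consequence differs by outcome. Counting losses as smokers gives every randomised participant an abstinence result. It does not supply a week-26 body weight or dietary recall. A null food-intake result, and to a lesser degree a null weight result, would be read against a detectable difference that 340 observed participants do not support.

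**Working it through.** **1. Can attrition explain the gap?**

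- 490 × 0.85 = 416.5 and 500 × 0.85 = 425. Neither is near 340; going from 490 to 340 needs a 31% loss.
- 490 is 426 × 1.15. Retaining 426 after a 15% loss needs 426/0.85 = 501.

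**2. How many would be randomised on the plan's figures?**

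| Route | Randomised | Left after 15% loss | Loss needed to reach 340 |
|---|---|---|---|
| 340/0.85 | 400 | 340 | 15% |
| 625 consents × 10/15 | 417 | 354 | 18% |
| 10 per month × 44 months | 440 | 374 | 23% |

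All three are below 490, and after 15% loss all are below 426. At 10 per month, 490 would take 49 months.

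**3. Abstinence (N = randomised).** Inputs from section 6.7: 13% against 25%, α = 0.025. I assume a two-sided test and that the two rates already count losses as smokers. The log odds ratio is ln[(0.25/0.75)/(0.13/0.87)] = 0.802, with SE = √[1/(n·0.13·0.87) + 1/(n·0.25·0.75)] for n per arm and critical value 2.241. The pooled z-test for two proportions is shown beside it.

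| Randomised | SE of log OR | Power, log OR | Power, pooled z |
|---|---|---|---|
| 426 | 0.258 | 80.8% | 82.3% |
| 400 | 0.266 | 78.0% | 79.6% |
| 417 | 0.261 | 79.8% | 81.4% |
| 440 | 0.254 | 82.1% | 83.6% |

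The stated 82% reproduces at 426.

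**4. Food intake (N = observed at week 26).** No SD is given, so I take the stated 80% for 320 kcal/day at α = 0.05 as correct at 426 and scale it. Detectable difference = 320 × √(426/N). Power = Φ[(1.960 + 0.842) × √(N/426) − 1.960]. Only the ratio N/426 matters, so the missing SD does not affect the result.

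| Observed | Detectable at 80% power | Power for 320 kcal/day |
|---|---|---|
| 340 | 358 kcal/day | 70.6% |
| 354 | 351 kcal/day | 72.4% |
| 374 | 342 kcal/day | 74.7% |

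**5. Weight (N = observed at week 26).** The test is the 2 × 2 interaction of arm and smoking status. SE = 3.5 × √(sum of 1/cell size), the effect is 2.72 kg and α = 0.025. The SD of 3.5 kg is stated in section 6.7 only for the exploratory aim. Cell sizes follow from 25% and 13% abstinence, with equal losses by arm.

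| Scenario | SE (kg) | Power for 6 lb | Detectable at 80% power |
|---|---|---|---|
| 426 observed | 0.903 | 78.0% | 6.1 lb |
| 340 observed of 400, only smokers lost (cells 50/26/120/144) | 0.950 | 73.3% | 6.5 lb |
| 340 observed of 417, only smokers lost | 0.936 | 74.7% | 6.4 lb |
| 340 observed of 440, only smokers lost (cells 55/28.6/115/141.4) | 0.919 | 76.4% | 6.2 lb |
| 340 observed, proportional loss | 1.011 | 67.4% | 6.9 lb |

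The stated 80% reproduces to within about 2 points. Scaling the stated figure directly, as for food intake, gives 6 × √(426/340) = 6.7 lb and 69.6% power under proportional loss.

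**The case against.** The strongest reply is that 340 and 426 count different groups. Section 4.4 reports about 80% retention through 12 weeks, and 340/0.80 = 425. So 426 could be the intention-to-treat sample and 340 those still attending. The documents do not say this, the 80% is a week-12 figure, and 490 would remain unexplained. Nor would it rescue food intake, which still has only 340 recalls.

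The lower randomised figures are softer than 440. The 400 applies section 6.7's attrition to section 4.2's completers. The 417 treats every consent as an Intake attendee, although current procedures can place consent and the IQ screen before that visit. This stands, but 440 comes directly from section 4.2 and also falls short.

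Weight is measured at every in-person visit, and section 6.10 proposes a longitudinal model with multiple imputation or all available data. Participants lost late would contribute something, so the observed-case figures are on the pessimistic side. Section 4.8.1 also does not forbid follow-up after withdrawal. However, section 6.10 leaves the missing-data method to be chosen after the missingness has been seen, and section 6.7 computes power by simple t- and z-approximations, so the plan does not quantify any recovery.

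Finally, abstinence, a primary outcome, is nearly unaffected, and weight loses only about 2 points in the best case (78.0% to 76.4%). The clearest shortfall is in a secondary outcome. That limits the damage but does not reconcile the three sections.

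**Conclusion.** The concern holds. The target of about 340 in sections 3.4 and 4.2 is incompatible with the 426 and 490 of section 6.7, and 15% attrition does not bridge them.

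- **Abstinence:** roughly as stated if about 440 are randomised, and 78–80% at 400. It would be wrong to compute this power on 340.
- **Food intake:** the stated 80% becomes about 71% at 340 observed, and about 75% even at 374. This assumes that the stated 80% refers to 426, as section 6.7 implies.
- **Weight:** 67–76% at 340 observed, depending on who is lost. This rests on the borrowed SD and on binary smoking status, whereas section 6.10 defines smoking status as days × rate. The direction is firm; the exact figure is not.

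**What to change.** State one randomised target and one week-26 evaluable target, identical in sections 3.4, 4.2 and 6.7 and consistent with about 10 per month over about 44 months. Then:

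- Restate abstinence power for the randomised number, saying whether the test is two-sided and whether 13% and 25% already count losses as smokers.
- Restate the food-intake and weight detectable differences for the evaluable number, giving the weight SD and the assumed loss pattern. If 340 is the evaluable number, food intake is about 358 kcal/day. On the assumptions above, weight is about 6.2–6.5 lb if losses fall among smokers, or 6.7–6.9 lb if they are proportional.
- Section 6.7 also states Aim 2 power for 426. Restate that mediator figure only for the number expected to have mediator data to week 8.

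This costs amended text and slightly less favourable stated power, with no extra patients. If the sponsor prefers to keep 426 evaluable, section 6.7's 15% attrition implies about 501 randomised, or about 50 months at 10 per month, and sections 3.4 and 4.2 must then be changed to say so.

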4.3 Accrual - Neuroimaging Sub-Study

Eligible participants enrolled in the parent study who meet the fMRI eligibility criteria will have the opportunity to participate in the neuroimaging sub-study. We estimate that in order to achieve a sample of ~50 participants who complete the neuroimaging sub-study with usable data, we will need to enroll ~75 participants into the sub-study. Accrual estimates are based on our extensive experience conducting neuroimaging studies and specifically recruitment of fMRI subsamples from larger clinical trials. To ensure retention, we: (1) educate subjects about the benefits of participation and knowledge gained from the study; (2) schedule sessions at convenient times; (3) provide reminder calls; and (4) provide incentives for completion of sessions and assessments. This accrual rate is highly feasible based on our prior work.

CONFIDENTIAL

This material is the property of the University of Pennsylvania. Do not disclose or use except as authorized in writing by the study sponsor

4.4 Accrual – Microbiome Sub-Study

Eligible participants enrolled in the parent study who meet the microbiome eligibility criteria will have the opportunity to participate in the microbiome sub-study. We estimate that in order to achieve a sample of up to 60 participants who complete the microbiome sub-study with usable data, we will need to enroll ~75 participants into the sub-study as our retention rate through 12 weeks is ~80%. To ensure retention in the sub-study, we will offer monetary incentives for providing stool samples per the study instructions.

